#### OBJ OBJ OBJ OBJ OBJ OBJ OBJ OBJ OBJ

Pitolisant effects on alcohol self administration and craving in heavy drinkers Version 1.10 7.7.2022 11.2 Source Documents

Source documents in this study include: Laboratory test results Photocopies of the urine drug screening test result ECG tracings Subject locator form Subject contact form

Data generated by the methods described in the protocol will be recorded in the subjects' source binder. Data may be transcribed legibly on CRFs for each subject or directly inputted into an electronic system or any combination thereof.

#### 11.3 Case Report Forms

The study case report form (CRF) will be the primary data collection instrument for the study. All data requested on the CRF will be recorded. All missing data will be explained. If a space on the CRF is left blank because the procedure was not done or the question was not asked, a written explanation will be included to detail why the data was not recorded. If the item is not applicable to the individual case, a notation will be made. All entries on will be printed legibly in black ink. If any entry error has been made, to correct such an error, a single straight line will be drawn through the incorrect entry and the correct data will be entered closely to the original data. All such changes will be initialed and dated. There will be no erasures or white-out on CRFs. For clarification of illegible or uncertain entries, the clarification will be printed near the item, then initialed and dated. Electronic CRFs in the REDcap system will include an audit trail.

The CRFs that will be used in this study are: Demographics **Concomitant Medications** Adverse Events Birth Control Assessment Urine Drug Screening Vital Signs Blood Alcohol Level Time-line Follow-back Pregnancy test Birth control assessment Medical History **Physical Examination** MINI diagnoses summary Medication Compliance log Eligibility ECG C-SSRS CIWA-AR **OCDS** 

11.4 Study Records Retention

Study records will be retained for at least seven years after completion of the study.

12 Statistical Plan

## 12.1 Study Hypotheses and Planned Analyses

HypothesisProposed Analyses1. Subjects will consume less alcohol during an alcohol self- administration trial when receiving pitolisant compared to when they are receiving placebo.The volume of alcohol consumed during alcohol challenge trials 1 and 2 will be used to test the effect of pitolisant on alcohol consumption. We will use a mixed models repeated measures approach to test for differences between alcohol consumed between the pitolisant and placebo self-administration trials45- 46. This data will be divided into first and second-hour blocks of self-administration. Within-subject factors for this analysis will include treatment and Time Block. Trial order will be used as covariate in these analyses to allow evaluation as to whether the order of treatments had a significant effect on the outcome. Appropriate covariance structures will be determined using

 
Subjects will consume less alcohol during an alcohol during an alcohol self-administration trial when receiving pitolisant compared to when they are receiving placebo.
 
The volume of alcohol consumed during alcohol challenge trials 1 and 2 will be used to test the effect of pitolisant on alcohol consumption. We will use a mixed models repeated measures approach to test for differences between alcohol consumed between the pitolisant and placebo self-administration trials45-46. This data will be divided into first and second-hour blocks of self-administration. Within-subject factors for this analysis will include treatment and Time Block. Trial order will be used as covariate in these analyses to allow evaluation as to whether the order of treatments had a significant effect on the outcome. Appropriate covariance structures will be determined using
 

 
less alcohol during an alcohol self-administration trial when receiving pitolisant compared to when they are receiving placebo.
 
1 and 2 will be used to test the effect of pitolisant on alcohol consumed between the pitolisant and placebo self-administration trials45-46. This data will be divided into first and second-hour blocks of self-administration. Within-subject factors for this analysis will include treatment and Time Block. Trial order will be used as covariate in these analyses to allow evaluation as to whether the order of treatments had a significant effect on the outcome. Appropriate covariance structures will be determined using
 


 
alcohol self-
 
administration trial when
 
receiving pitolisant
 
compared to when they
 
are receiving placebo.
 
are receiving placebo.
 
compared to when they
 
are receiving placebo.
 
are receiving placebo.
 
compared to when they
 
are receiving placebo.
 
compared to when they
 
are receiving placebo.
 
are receiving placebo.
 
between the pitolisant and placebo self-administration trials45-
 
46. This data will be divided into first and second-hour blocks of
 
self-administration. Within-subject factors for this analysis will
 
include treatment and Time Block. Trial order will be used as
 
covariate in these analyses to allow evaluation as to whether the
 
order of treatments had a significant effect on the outcome.
 
Appropriate covariance structures will be determined using
 

 
administration trial when receiving pitolisant compared to when they are receiving placebo.
 
approach to test for differences between alcohol consumed between the pitolisant and placebo self-administration trials45-46. This data will be divided into first and second-hour blocks of self-administration. Within-subject factors for this analysis will include treatment and Time Block. Trial order will be used as covariate in these analyses to allow evaluation as to whether the order of treatments had a significant effect on the outcome. Appropriate covariance structures will be determined using
 

receiving pitolisant compared to when they are receiving placebo.

 
compared to when they are receiving placebo.
 
46. This data will be divided into first and second-hour blocks of self-administration. Within-subject factors for this analysis will include treatment and Time Block. Trial order will be used as covariate in these analyses to allow evaluation as to whether the order of treatments had a significant effect on the outcome. Appropriate covariance structures will be determined using
 

are receiving placebo. self-administration. Within-subject factors for this analysis will include treatment and Time Block. Trial order will be used as covariate in these analyses to allow evaluation as to whether the order of treatments had a significant effect on the outcome. Appropriate covariance structures will be determined using
include treatment and Time Block. Trial order will be used as covariate in these analyses to allow evaluation as to whether the order of treatments had a significant effect on the outcome. Appropriate covariance structures will be determined using
covariate in these analyses to allow evaluation as to whether the order of treatments had a significant effect on the outcome. Appropriate covariance structures will be determined using
order of treatments had a significant effect on the outcome. Appropriate covariance structures will be determined using
Appropriate covariance structures will be determined using
Akaikes information criteria to evaluate the best model fit.
Results analysis will be examined for both treatment effects and
the Treatment x Time Block interaction results.
2. Subjects will report Craving measures (AUQ and VAS) collected at 30-minute
lower levels of craving as intervals during the self-administration trials will be used to test
measured by the Visual the effect of pitolisant on alcohol craving. A mixed models
Analog Scale (VAS) and approach will be used to test for differences in craving between
the Alcohol Urge the pitolisant and placebo self-administration trials. Within-
questionnaire (AUQ) subject factors for this analysis will include Treatment and Time
during the pitolisant self- Block. Trial order will be used as covariate in these analyses to
administration trial allow evaluation as to whether the order of treatments has a
compared to the placebo significant effect on the outcome.
self-administration trial.
3. Subjects will BAES scores and BALs obtained during the 40-minute
experience no difference observation period and both of the 60-minute self-administration
in alcohol-induced blocks will be used to test the effect of pitolisant on the
stimulation, as measured stimulating effects of alcohol. A mixed model for repeated
on the BAES, after the measures approach will be used to test for differences between
consumption of the pitolisant and placebo on the stimulant BAES scores at each of
priming dose of alcohol the 10-minute observation intervals and 30-minute self-
when they are receiving administration intervals. This data will be analyzed with
pitolisant as compared to Treatment and Time used as within-subject factors.
when they are receiving
placebo.
5. Subjects will report The alcohol VAS, OCDS, and the TLFB measurements during
lower levels of alcohol the twelve-day period of drug exposure will be used to determine

For our primary outcomes, separate analyses will be conducted on data collected during the Priming and Self-Administration periods of the test session.

during pitolisant exposure	models repeated measures approach will be used to test for		
period as compared to	differences in craving and consumption between the pitolisant		
placebo exposure period.	and placebo trials. Treatment will be used as within-subject		
	factor. VAS measures taken on each of the twelve days of drug		
	exposure, repeated measures mixed models analysis will be		
	conducted with Day and Treatment as within-subject factors.		
6. Subjects will not report	Daily hours of sleep and number of minutes spent awake during		
significant differences in	the twelve-day period of drug exposure will be used to determine		
the number of hours sleep	the effect of pitolisant on craving and consumption. Mixed		
per night and minutes	Models repeated measures approach will be used to test for		
spent awake during the	differences in sleep quality between the pitolisant and placebo		
pitolisant exposure period	trials. Treatment will be used as within-subject factor. Sleep		
as compared to the	measures taken on each of the twelve days of drug exposure,		
placebo exposure period	repeated measures mixed models analysis will be conducted with		
	Day and Treatment as within-subject factors.		

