Design/Methodology:	This is a double-blind, randomized, placebo-controlled, crossover design trial that will test the effect of pitolisant on alcohol self-administration and craving following a priming dose of alcohol. An established human laboratory self- administration procedure will be followed. Each subject will complete 5 clinic visits over a period of up to 66 days of participation. Study participation is comprised of a baseline assessment, randomization visit, alcohol self administration Trial 1, an assessment visit to verify continued eligibility and dispense medication, and a second alcohol self-administration Trial. The volume of alcohol consumed during alcohol challenge trials 1 and 2 will be used to test the effect of pitolisant on alcohol consumption. Craving measures (AUQ and VAS) collected during the self-administration trials will be used to test the effect of pitolisant on alcohol craving.
Total Study	The entire study will take 24 months to complete.
Duration:	
Subject Participation	Each subject's length of participation will be up to 66 days.
Duration:	

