defined as  $\geq$  35 standard drinks per week for men, and  $\geq$  28 standard drinks per week for women. This stratified randomization will minimize the possibility that the order of study drug administration seems to influence outcomes when order effects are actually related to differences in severity of drinking between the two groups of subjects who are receiving the study medication in a different order. On the day of randomization, subjects will undergo an alcohol breath test, urine drug screening, urine pregnancy testing, assessment of concomitant medications, and the TLFB to ensure eligibility. Subjects who have purposefully abstained from drinking and achieved 14 days of abstinence prior to the challenge will be discontinued from participation for ethical reasons. Eligible subjects will be randomized and will receive a 12-day supply of over-encapsulated pitolisant or a matched placebo. Subjects will be scheduled for an alcohol challenge trial within 19 days of randomization. Subjects will be contacted to remind them to start taking study medication twelve days prior to the scheduled alcohol challenge trial. Subjects will be allowed to delay start of medication for up to 7 days after randomization in order to accommodate scheduling for the alcohol challenge trial.

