### Medication Visit #2

After the 7-14 day washout period subjects will return to the lab to receive study medication prior to the alcohol challenge #2. Subjects will complete the same tests and interviews completed during the randomization visit (See appendix A for schedule of events). Based on the assessments at medication visit #2, subjects be discontinued for the following reasons: pregnancy, recreational drug use except for marijuana, evidence of non-compliance with study medication, suicidal thoughts or behavior, and use of a new medication that would make participation unsafe. Subjects will receive a 12-day supply of study medication and will be scheduled for the alcohol challenge #2. Subjects will be allowed to delay start of medication for up to 7 days after randomization in order to accommodate scheduling for the alcohol challenge trial.

Alcohol Challenge Trials 1 & 2: Subjects will return to the laboratory on day 12 of drug exposure for each medication trial to complete the alcohol challenge. For safety reasons, subjects will be asked to arrange transportation plans (no driving) prior each of the alcohol challenge trials. There will be a 7-14 day washout period between alcohol challenge Trial 1 and medication visit #2. The washout may extend to 14 days to accommodate the scheduling of the medication visit. Concomitant medications, urine drug screening, urine pregnancy testing, blood alcohol level will be assessed to determine eligibility to proceed with the challenge. Blood alcohol level must be 0.000 to continue with the study procedures. Urine collected for drug screening will be exposed to ultraviolet light as an objective test of medication compliance. If no fluorescence is observed in the urine sample the subject will be excluded from continuing with the challenge. Measures of drinking (TLFB) and cravings (OCDS, VAS and AUQ) will be collected to inform secondary outcomes. Subjects will be observed taking the morning dose of pitolisant (or placebo) on the day of the challenge (after compliance is confirmed via a urine screening). The peak plasma concentration of pitolisant should be reached approximately 60 minutes after administration. The alcohol self-administration session will begin no sooner than one hour after the administration of the observed 17.8 mg morning dose. The alcohol selfadministration will be conducted in the GCRU. The room will be a carpeted and furnished with

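### In this two-period crossover the models for H3, H5 and H6 have no Trial 1 versus Trial 2 (Period) term, and the Trial order term in H1 and H2 is not coded as Period or Sequence

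*Combined protocol and SAP*

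**What the plan says.** Section 9 (Study randomization) sets up two groups of 18, one receiving pitolisant before the first alcohol challenge and the other before the second. This is a two-sequence, two-period crossover.

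Section 12.1 describes the models row by row:
- **H1 (alcohol consumed):** Treatment, Time Block and an order term: "Trial order will be used as covariate in these analyses to allow evaluation as to whether the order of treatments had a significant effect".
- **H2 (craving in the session):** Treatment, Time Block and the same order term.
- **H3 (BAES):** "Treatment and Time used as within-subject factors". Time is the 10- and 30-minute assessment grid.
- **H5 (VAS, OCDS, TLFB during exposure):** Treatment, and for the daily VAS "Day and Treatment as within-subject factors".
- **H6 (sleep):** "Treatment will be used as within-subject factor", with Day added for the daily measures.

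Day is the day within a 12-day exposure period and Time is the minute within a session, so neither stands for Trial 1 versus Trial 2. The H5 row is broken in the extracted text, but the sentences listing its model terms can still be read.

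On what Trial order means, the document points both ways. Elsewhere it numbers the two periods as trials (section 2: "The volume of alcohol consumed during alcohol challenge trials 1 and 2 will be used to test the effect of pitolisant on alcohol consumption"; section 9: "There will be a 7-14 day washout period between alcohol challenge Trial 1 and medication visit #2"), which suggests Period. The purpose given in the H1 row is the order of treatments, and section 9 speaks of "order effects are actually related to differences in severity of drinking between the two groups", which suggests Sequence.

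**The concern.** Each treatment difference in a crossover is also a difference between Trial 1 and Trial 2. Responses can change between the two trials for reasons unrelated to the drug, such as familiarity with the laboratory or habituation to daily reporting. A Period term removes that change from the treatment contrast. Sequence does not: it is constant within a subject, and with complete data it leaves the within-subject contrast as it was.

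Two things are at stake. If the sequences finish with unequal numbers, an unmodelled period change biases the treatment estimate. If the fitted covariance has a subject-by-trial component, the change also goes into the error term, which widens the interval and makes the test conservative. H3 and H6 predict no difference, so in those rows a conservative test leans towards the predicted result. For H1 and H2 the same issue arises only if Trial order is coded as Sequence.

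**Working it through.** **Inputs.** Sections 9 and 12.2 give 18 per sequence, 36 randomised, 28 completers, a difference of 1.5 drinks, an SD of within-subject differences of 2.1, an effect size of 0.7, alpha 0.01 and power 0.81. The documents give no period shift and no SD for BAES, VAS, OCDS, TLFB or sleep. Shifts are therefore assumed, in units of the SD of the within-subject difference in trial means.

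**1. The plan's own figure.** Paired t, noncentral t with 27 df, two-sided alpha 0.01 (sidedness is not stated), n = 28. Power is 0.815 at effect size 0.70 and 0.834 at 1.5/2.1 = 0.714. The stated 0.81 reproduces.

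**2. Bias without Period.** Let π be the Trial 2 minus Trial 1 shift, n1 the completers with pitolisant first and n2 those with it second. The pitolisant-minus-placebo difference has mean τ − π in the first group and τ + π in the second. The overall mean is τ + π(n2−n1)/N, so the absolute bias is |π| × |n1−n2|/N.
- 14/14: 0.
- 15/13: 2/28 = 0.071 × shift.
- 16/12: 4/28 = 0.143 × shift. For shifts of 0.25 and 0.5 SD this is 0.036 and 0.071 SD, or 19% and 38% of one standard error (1/√28 = 0.189 SD).

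The formula needs a covariance that treats the two trials symmetrically. Exact generalised least squares at 16/12, complete data, no order term, gives smaller factors in the asymmetric structures checked:

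| Structure | Bias ÷ shift |
|---|---|
| Symmetric in trial | 0.143 |
| Variance 2:1 by trial, correlation 0.5 | 0.123 |
| Variance 4:1 by trial, correlation 0.5 | 0.082 |
| AR(1) over 24 daily records, ρ = 0.5 / 0.8 / 0.95 | 0.135 / 0.084 / 0.036 |

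**3. Precision without Period.** With a subject-by-trial component, the variance of the paired differences becomes SD² + π² × 4n1n2/[N(N−1)]. With Period, SE = (SD/2)√(1/n1 + 1/n2) on N−2 df. Test size is by simulation at an assumed alpha of 0.05.

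| Split | Shift (SD) | Bias (SD) | CI width, without ÷ with Period | Test size |
|---|---|---|---|---|
| 14/14 | 0.25 | 0 | 1.03 | 0.043–0.044 |
| 14/14 | 0.5 | 0 | 1.12 | 0.028 |
| 16/12 | 0.25 | 0.036 | 1.02 | 0.046 |
| 16/12 | 0.5 | 0.071 | 1.11 | 0.040 |

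Example at 14/14 with a 0.5 SD shift: √(1 + 0.25 × 784/756) = 1.122. The change from 27 to 26 df brings the ratio to 1.12.

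With a random intercept only, simulated CI widths at a 0.5 SD shift were 0.748 against 0.742 (8 time points) and 0.746 against 0.741 (12 days) with no subject-by-trial variance. They were 0.447 against 0.436 and 0.433 against 0.425 when that variance was 70% of the total. The widening is about 2.5% or less.

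**4. H1, only if Trial order means Sequence.** At 16/12 a 0.5-drink shift biases the estimate by 0.143 × 0.5 = 0.07 drinks, and a 1.0-drink shift by 0.14. In a mixed model fitted to simulated 16/12 data, adding Sequence alone left the treatment estimate and SE unchanged (−1.307, SE 0.358). Adding Period changed both (−1.156, SE 0.304).

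**5. How likely is imbalance?** If 28 of 36 complete at random (hypergeometric, 18 per group), a 16/12 or worse split has probability 0.23, 15/13 or closer 0.77, and 18/10 0.003.

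**The case against.** The strongest reply is that the effect is small and hypothetical. Allocation is equal and the contrast is within subject. Under random completion the split is 15/13 or closer with probability 0.77, and there the bias is at most 0.5 × 0.071 = 0.036 SD even for the larger assumed shift. All of this stands and limits the size of the point. It does not explain why three of the five models lack a term that the other two may have.

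A reader might also infer more than the documents support:
- **That the primary analyses ignore period.** H1 and H2 carry Trial order, and the numbering of the trials makes Period a natural reading. Only the coding is missing.
- **That the bias formula holds under any covariance.** It does not. Section 12.1 leaves the H1 structure to AIC and fixes none for H3, H5 or H6, and the asymmetric structures checked gave less bias.
- **That bias and the full loss of test size occur together.** The size of 0.028 belongs to 14/14, where bias is zero. At 16/12 the same shift gives 0.040.
- **That 28 completers or power 0.81 is wrong.** Both reproduce.
- **That Period would make a non-significant H3 or H6 result evidence of no difference.** It would not.

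A last objection is that recoding Trial order as Period would drop the stated aim of examining treatment order. That is fair, and it is why Sequence should stay as a term of its own.

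**Conclusion.** The point holds in limited form. As written, the H3, H5 and H6 models are not adjusted for Trial 1 versus Trial 2. H1 and H2 may or may not be, because the coding of Trial order is not given. The consequence depends on a period shift that the documents do not state. For shifts of 0.25 to 0.5 SD it ranges from no bias and a 3–12% wider interval at 14/14 (subject-by-trial covariance) to a bias of 0.036–0.071 SD at 16/12 (symmetric covariance). The cost in precision is much less under a random intercept alone. The sponsor should make the change because it is cheap and settles the coding before any data are seen.

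**What to change.** In section 12.1:
- Add Period (Trial 1, Trial 2) as a within-subject fixed effect to the H3, H5 and H6 models.
- State that the H1 and H2 models include Period.
- Keep Sequence (pitolisant first, pitolisant second) as a separate, descriptive between-subject term, so that the planned look at order of treatments is retained. Say that in a two-by-two design it is aliased with carryover and that its test will not decide which analysis is used.
- Take the treatment effect from the period-adjusted contrast in every model. Time Block, Time and Day stay as planned.

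The cost is a sentence or two of wording and one degree of freedom for Period. Trial number is already recorded. H1 power with Period, 28 completers and two-sided alpha 0.01:

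| Completers | Effect size 0.70 | 1.5/2.1 |
|---|---|---|
| No Period term | 0.815 | 0.834 |
| 14/14 | 0.813 | 0.831 |
| 16/12 | 0.803 | 0.822 |
| 18/10 (probability 0.003) | 0.772 | 0.792 |

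At the stated effect size of 0.7, power falls just below 0.81 at 16/12. That is a small cost under imbalance and no reason to change the planned 28 completers.

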#### 5 Study Design

This is a double-blind, randomized, placebo-controlled, crossover design trial that will test the effect of pitolisant on alcohol self-administration and craving following a priming dose of alcohol. An established human laboratory self-administration methodology developed by O'Malley and her colleagues will be followed. The O'Malley self-administration methodology entails subjects consuming a priming drink of alcohol and subsequently participating in two one-hour self-administration sessions. In each session subjects receive four alcoholic drinks which

they may either drink, or otherwise receive compensation for not consuming. Confirmation of the validity of this approach as a method for screening for medications to treat AUD include the finding that pre-treatment with naltrexone significantly reduced alcohol consumption when the O'Malley methodology was used. Using this method, our group has found that the anticonvulsant zonisamide reduces alcohol consumption in non-treatment seeking social drinkers. We later confirmed that the administration of zonisamide decreases alcohol consumption in subjects with AUD in a double-blind randomized clinical trial as have other investigators. Testing pitolisant using this self-administration methodology is the next logical step in drug development given the strong evidence that the H-3 receptor inverse agonist/antagonists reduce drinking in animal models. The human laboratory-based alcohol self-administration methodology is cost effective and time-efficient for testing novel drug candidates for AUD treatment.

*Subjects:* Heavy-drinking subjects will be enrolled to increase the potential generalizability of these findings to a clinical AUD population. Subjects will be recruited through advertising, study flyers, internet postings, and an established subject registry at Boston Medical Center. Interested subjects will be screened by telephone to determine initial eligibility prior to the baseline assessment.

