### 12.2 Sample Size Determination

A group size of 28 completers was selected for use in this study based on an assumed effect size of 0.7 suggested by similar alcohol self-administration studies with amount consumed as the primary outcome. This effect size is in the range we found for the anticonvulsant zonisamide used in a similar alcohol self-administration study. The sample size for this study is based on an estimated reduction of 1.5 standard drinks with an estimated standard deviation (2.1) of the between Challenge Trial differences in alcohol self-administration, with an effect size of this magnitude (i.e. 0.7). This requires a sample size of 28 to allow for detection of a significant within-subject difference in alcohol consumption with an alpha value of 0.01 and power value of 0.81. Based on an estimated 15-20% rate of non-completion for randomized subjects, we anticipate randomizing 36 subjects to achieve a sample of 28 completers. Given our experience with recruiting AUD populations into clinical trials, we expect a screening exclusion rate of roughly 50%. Approximately 72 subjects will be consented and screened in clinic to yield a sample of 36 eligible subjects. Given that this a laboratory based experiment we do not plan to conduct any planned interim analyses in this study.

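### The AIC rule for the primary consumption model does not require a session-level effect, so it can select a covariance structure that understates the standard error of the treatment contrast.

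*Combined protocol and SAP*

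**What the plan says.** Section 5 describes a "double-blind, randomized, placebo-controlled, crossover design trial", so each subject has one alcohol session on each treatment. For consumption, section 12.1 (hypothesis 1) states: "This data will be divided into first and second-hour blocks of self-administration". It continues: "Within-subject factors for this analysis will include treatment and Time Block", and "Trial order will be used as covariate in these analyses". The treatment effect and the Treatment by Time Block interaction are both to be examined.

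On the error structure the plan has one sentence: "Appropriate covariance structures will be determined using" "Akaikes information criteria to evaluate the best model fit". No candidate structures, subject-by-session term, degrees-of-freedom method or fallback are given.

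Section 12.2 bases the sample size on an SD of 2.1 for the "between Challenge Trial differences in alcohol self-administration", "with an alpha value of 0.01 and power value of 0.81".

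**The concern.** Each subject contributes four values: two blocks in each of two sessions. Treatment is constant within a session, so the right error for the treatment main effect is the variation of the between-session difference within a subject. Section 12.2 uses exactly that quantity.

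The two blocks of a session share the day, the priming drink and the observed dose (section 9). Session-specific variation that affects both is therefore plausible. If it exists and the fitted structure has no term for it, the second block is counted partly as fresh information about treatment.

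The AIC rule does not prevent this. Unstructured has 10 parameters and compound symmetry 2, so unstructured must lower minus twice the log-likelihood by more than 2 × (10 − 2) = 16 to be chosen. At stake is the error rate of the primary consumption test, and its agreement with the paired calculation behind the stated power.

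**Working it through.** **1. The plan's own figure.** Inputs from section 12.2: effect size 0.7 (1.5/2.1 = 0.714), 28 completers, alpha 0.01. The test is taken as two-sided, which the plan does not state. For a paired t-test with 27 df the noncentrality is 0.7 × √28 = 3.70, giving power 0.815 against the stated 0.81. With 0.714 the power is 0.834. A one-sided test gives 0.883, which does not match. The sample size is thus a paired calculation on session differences and it reproduces. The standard error it implies is 2.1/√28 = 0.397 drinks.

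**2. How compound symmetry goes wrong.** Let b be the subject-by-session variance, c the residual variance and ρ = b/(b + c), the within-session correlation beyond the subject effect. Per subject, the difference of session means has variance 2b + c. Compound symmetry pools this contrast with two others that have expected mean square c, and so uses (2b + 3c)/3 = c + 2b/3. Hence

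model SE / true SE = √[(1 − ρ/3)/(1 + ρ)].

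| ρ | ratio | SE used (true 0.397) |
|---|---|---|
| −0.2 | 1.155 | 0.458 |
| 0 | 1.000 | 0.397 |
| 0.2 | 0.882 | 0.350 |
| 0.3 | 0.832 | 0.330 |
| 0.5 | 0.745 | 0.296 |

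This shows the direction when compound symmetry is fitted. It is not the result of the plan's rule, which selects among structures.

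**3. What AIC selection gives.** Simulation with no treatment effect, 28 subjects, four normal values each, REML fits, and AIC over compound symmetry, AR(1) and unstructured (81, 54 and 27 df). The correlations are assumptions. With total within-session correlation w and between-session correlation r, ρ = (w − r)/(1 − r). The settings w 0.6 to 0.8 and r 0.4 to 0.5 span ρ = 0.1/0.5 = 0.20 to 0.4/0.6 = 0.67.

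| Analysis | at 0.01 | at 0.05 |
|---|---|---|
| AIC over the three structures | 0.016–0.022 | 0.062–0.074 |
| Unstructured or nested (subject plus subject-by-session), fixed in advance | 0.008–0.011 | 0.046–0.053 |
| AIC with the nested structure added | 0.011–0.015 | 0.047–0.065 |
| AIC over the three, w = r = 0.5 | about 0.01 | 0.041–0.05 |
| AIC over the three, w = 0.4, r = 0.5 | 0.006 | 0.033 |

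Monte Carlo error is about 0.001 to 0.002 at the 0.01 level. One repeat of the first row reached 0.026 and 0.083. In a separate run over a wider list (heterogeneous compound symmetry added, 80 and 26 df), AIC with the nested structure available gave 0.017 to 0.019 for ρ from 0.1 to 0.7. In that run, unstructured with unadjusted standard errors gave 0.018 to 0.021, which is why the small-sample method should be named as well.

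**4. After the fix.** With the session effect fixed in the model, the standard error returns to 0.397 drinks. Power at 28 completers is 0.815 (27 df) or 0.813 (26 df).

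**The case against.** The strongest reply is that the plan asks for appropriate structures and names Treatment and Time Block as within-subject factors. A competent analyst could therefore include a subject-by-treatment random effect, and AIC would then often find it. That stands in part: with such a candidate the error is close to nominal. But nothing in the text requires it.

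The direction is also not fixed. With equal correlations there is no inflation, and with a lower within-session correlation the test is conservative. The documents give no within-session correlation. Each block is capped at four drinks, so the data will not be normal as simulated. These limits stand, and make the size conditional.

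Several stronger readings are tempting and not supported:

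- A reader might infer that AIC usually picks a simple structure. At within-session correlation 0.8 it chose unstructured in 56 to 73% of runs.
- A reader might put AR(1) alongside compound symmetry. The formula above covers compound symmetry only, and AR(1) used alone was nominal or conservative in several settings.
- A reader might quote error rates for compound symmetry used throughout. The plan does not fix that structure, and where it is worst AIC picked it in only about 2 to 5% of runs.
- A reader might extend the point to the craving, BAES and daily-diary models. The AIC sentence stands under hypothesis 1 only, and no calculation was made for the others.

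**Conclusion.** The gap is real and concerns the primary consumption test. The selection rule in section 12.1 can deliver a treatment contrast whose standard error omits part of the session-level variation. Under the assumed correlations and the three-structure list, type I error is about 1.6 to 2.2 times nominal at 0.01 (0.016 to 0.022) and about 0.06 to 0.075 at 0.05.

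This rests on a positive within-session correlation beyond the subject effect and on a candidate list without a session-level random effect. The documents state neither. It would be too strong to say that the primary test will miss its nominal level. What the documents support is that nothing in the plan secures that level. A reader might also infer that 28 completers is the wrong number; it is not, since the paired calculation reproduces.

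**What to change.** In section 12.1, hypothesis 1, replace the covariance sentence with a fixed choice for the treatment test: random subject and random subject-by-session effects, or an unstructured 4 × 4 matrix, with Kenward-Roger degrees of freedom. Alternatively, test treatment on the within-subject difference of session totals, which is the analysis that section 12.2 powers. AIC may stay if it chooses only among structures that retain the session effect.

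The cost is one or two sentences and no extra subjects. The test has fewer error degrees of freedom (about 27 instead of 81). If there is truly no session-level variation, the random-effects version is slightly conservative: 0.005 at nominal 0.01 and 0.038 at 0.05 in simulation with ρ = 0. The session-total version uses only subjects with both sessions, whereas the mixed model can keep a subject with one.
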